8.3. Additional Secondary Efficacy Endpoints and Analyses

8.3.1. CFB in OAB-q LF Scores at Week 12

The OAB-q LF Total HRQL Score is detailed in [Section 8.2.6](#). The CFB analysis for the Total HRQL Score at Week 12 will be calculated and analyzed in the same manner as described above in [Section 8.2.6](#). More specifically, the primary inference will be drawn from the treatment difference between vibegron and placebo at Week 12. The standard error and 95% CI for the difference will also be presented with the corresponding p-value; these will also be presented for the difference between tolterodine and placebo. Additionally, estimates of least-squares means, standard errors, and 95% CIs will be presented for each treatment group.

The OAB-q LF Symptom bother Score is detailed in [Section 8.2.6](#). The CFB analysis for the Symptom Bother Score at Week 12 will be calculated and analyzed in the same manner as described above in [Section 8.2.6](#). More specifically, the primary inference will be drawn from the treatment difference between vibegron and placebo at Week 12. The standard error and 95% CI for the difference will also be presented with the corresponding p-value; these will also be presented for the difference between tolterodine and placebo. Additionally, estimates of least-squares means, standard errors, and 95% CIs will be presented for each treatment group.

The FAS will be the analysis population for the all of the OAB-q LF endpoints.

8.3.2. Responder Endpoints

The following are additional secondary responder endpoints:

- Percent of all OAB patients with average daily number of micturitions < 8 at Week 12

- A patient is defined as having an average of < 8 daily micturitions if the arithmetic mean of the number of micturitions per day in the void diary is less than 8 in a voiding diary.
- The FAS is the analysis set for this endpoint. Imputation of missing data will be performed using MI.
- Percent of OAB Wet patients with at least a 50% reduction from baseline in average daily number of incontinence episodes at Week 12
 - This endpoint is derived in the same manner as [Section 8.2.3](#) but uses all events marked as having leakage, regardless of cause, or where “Accidental Leakage” is checked.
 - The FAS-I is the analysis set for this endpoint. Imputation of missing data will be performed using MI.

[figure not shown]
[figure not shown]
All of the above endpoints will be analyzed in the same manner as described above in [Section 8.2.3](#).

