4.3. Additional Secondary Efficacy Endpoints

The additional secondary efficacy endpoints for this study are as follows:

- CFB at Week 12 in Health-related Quality of Life (HRQL) Total Score from the OAB-q LF (1-week recall) in all OAB patients
- CFB at Week 12 in Symptom Bother Score from the OAB-q-LF (1-week recall) in all OAB patients
- Percent of all OAB patients with average number of micturitions < 8 per 24 hours at Week 12
- Percent of OAB Wet patients with at least a 50% reduction from baseline in total incontinence episodes per 24 hours at Week 12
- CFB at Week 12 in overall bladder symptoms based on Patient Global Impression of Severity (PGI-Severity) in all OAB patients
- CFB at Week 12 in overall control over bladder symptoms based on Patient Global Impression of Control (PGI-Control) in all OAB patients

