OAB Wet: Patients are considered OAB Wet according to the following criteria:

- An average of ≥ 8.0 micturitions per Diary Day; and,
- An average of ≥ 1.0 UUI episodes per Diary Day; and,
- If stress urinary incontinence (SUI) is present, the total number of UUI episodes must be greater than the total number of SUI episodes.

OAB Dry: Patients are considered OAB Dry according to the following criteria:

- An average of ≥ 8.0 micturitions per Diary Day; and,
- An average of ≥ 3.0 urgency episodes per Diary Day; and,
- An average of < 1.0 UUI episodes per Diary Day

OAB-d Type Missing: Patients are considered non-categorized for OAB if neither of the above criteria is achieved.

Where OAB Wet is discussed in this document, it pertains to patients randomized under the strata of OAB Wet; where all OAB Patients are discussed, this relates to all patients randomized as either OAB Wet or OAB Dry. Under the randomization strata, all patients are categorized as OAB Wet or Dry; missing is not present. Unless otherwise stated, for the purposes of the analyses, OAB Type (i.e. as randomized) will be used.

Diary Day

A “Diary Day” is defined as the time between when the patient gets up for the day each morning and the time the patient gets up for the day the next morning as recorded in the patient voiding diary.

Complete Diary Day

A “Complete Diary Day” is defined as a Diary Day that includes input of micturition data by patients on the voiding diary. Unless a patient indicated “No” to the questions of “Did you record each time you urinated or leaked during this Diary Day” the Diary Day is considered complete.

For post-baseline diaries at Weeks 4 and 8, only complete diary days within 10 days prior to the study visit will be included. For the Week 12/Early Termination diary, only complete diary days within 14 days prior to the study visit will be included. For the Week 2 diary, complete diary days within 10 days prior to the target Week 2 day will be used. For diaries at all visits, if a patient has fewer than 4 complete diary days, that will be identified as a significant protocol deviation and that diary data will be excluded from all analysis.

Definition of Baseline for Patient Voiding Diary Endpoints

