Baseline will be the data collected during the Run-in Period. If greater than 10 complete diary days are available in the Run-in diary, only the complete diary days within the 10 days prior to the Baseline visit will be used; if 4 or more and less than 10 complete diary days are available, all complete diary days in the Run-in diary will be used to calculate Baseline. If less than 4 complete diary days are available, the Baseline will be regarded as missing. For a patient to have an evaluable change from baseline, the patient must have both a baseline diary and a post-baseline diary from any post-baseline timepoint, after analysis window has been applied (i.e., Week 2, Week 4, Week 8, or Week 12).

Definition of Baseline for Endpoints not Derived from the Patient Voiding Diary

Baseline value for all secondary efficacy, exploratory and safety endpoints will be defined as the last non-missing assessment before starting double-blind treatment.

Screening/Washout Period

The Screening/Washout Period covers Day -49 (Screening Visit) to Day -15 (the day before the start of the Run-in Period), which includes a 28-day washout period followed by 7-days of Diary completion. Patients not requiring the 28-day washout period can begin the 7-day Diary the day after the Screening Visit.

Run-in Period

The Run-in Period covers the duration between screening (Day -14) and the day before baseline (Day 1). There is no day 0 included in the study.

Treatment Period

The Treatment Period covers the duration that a patient is in the study from Baseline (Day 1) and Week 12.

Safety Follow-up Period

The Safety Follow-up Period continues for 28 days after the last dose of study treatment (Day 85) through Day 113 (Follow-up Visit).

Definition of Study Completion

A patient will be defined as “completed” if she/he completes the Week 12 study visit.

End of Study Definition

End of study is defined as the date when the patient has completed one of the following: completed the follow-up visit after the Week 12 visit, enrolled into the extension trial 3004, permanently discontinued from the study, or lost to follow-up. When lost to follow-up, the latest date of assessment/event in the database will be used as the last known date of the patient in study.

Day of Study Event (Post-Randomization)

Day of study event = Event Date – Date of Randomization (Day 1) + 1.

Day of Study Event (Pre-Randomization)

Day of study event = Event Date – Date of Randomization (Day 1).

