8.1.1.1. Primary Analysis

A mixed model for repeated measures (MMRM) with restricted maximum likelihood estimation will be used as the primary analysis model for change from baseline in average number of daily micturitions at Week 12. This model includes data from Week 2, Week 4, Week 8 and Week 12 and corrects for data that is missing at random (MAR), accounting for the fact that measurements taken on the same patient over time tend to be correlated, by using all available information on patients within the same covariate set to derive an

estimate of the treatment effect for a MAR-free population. No imputation of missing data is required for this analysis. The analysis model will include terms for treatment, visit, OAB Type (Wet vs Dry), Sex (Female vs Male), Region (US vs non-US), baseline score, and interaction of visit by treatment.

Primary inference will be drawn from the treatment difference between vibegron and placebo at Week 12. The comparisons between tolterodine and placebo will be reported with nominal p-values. The standard error and 95% CI for the differences will also be presented with the corresponding p-values. Additionally, estimates of least-squares means, standard errors, and 95% CIs will be presented for each treatment group (placebo, vibegron and tolterodine). The table output will also include treatment group estimates and treatment differences between vibegron and placebo, and tolterodine and placebo at Weeks 2, 4, and 8 from this model.

An unstructured covariance matrix will be used to model the correlation among repeated measurements. The Kenward-Roger adjustment will be used with restricted (or residual) maximum likelihood (REML) to make statistical inference. If the unstructured covariance model fails to converge with the default Newton-Raphson algorithm, the Fisher scoring algorithm will be used to provide initial values of the covariance parameters. In the rare event that none of the above methods yield convergence, the following structures will be investigated: heterogeneous Toeplitz, Toeplitz, heterogeneous First-Order Autoregressive [AR (1)], heterogeneous compound symmetry (HCS), and compound symmetry (CS). The covariance structure converging to the best fit, as determined by Akaike's information criterion (AIC), will be used.

An example of the SAS code for the base procedure is given below:

```
proc mixed data = datain method = reml ;
  class TRTP AVISITN USUBJID OABTYPE SEX REGION ;

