Where *aval* is the value at Week 12 and *base* is the baseline value. The achievement of at least a 75% reduction in UUI episodes (and similarly, a 100% reduction in UUI episodes) is a binary variable of 0 (endpoint is not attained) or 1 (endpoint is attained). The difference in proportion responding between vibegron and placebo, and tolterodine and placebo along with the associated 95% confidence interval and p-value, will be calculated using the Cochran-Mantel-Haenszel risk difference estimate stratified by Sex (Female vs Male), with weights proposed by Greenland and Robins, which is calculated as follows:

$$\hat{\delta}_{MH} = \frac{\sum_{i=1}^u w_i \cdot \hat{\delta}_i}{\sum_{i=1}^u w_i}, \text{ where}$$

$$\hat{\delta}_i = \frac{x_i}{n_i} - \frac{y_i}{m_i} \text{ denotes the risk difference in stratum } i, i = 1, \dots, u$$

$$w_i = \frac{n_i \cdot m_i}{n_i + m_i} \text{ denotes the weight of stratum } i, i = 1, \dots, u$$

x_i denotes the number of patients with event in treatment₁ in stratum $i, i = 1, \dots, u$

y_i denotes the number of patients with event in treatment₂ in stratum $i, i = 1, \dots, u$

n_i denotes the number of patients on treatment₁ in stratum $i, i = 1, \dots, u$

m_i denotes the number of patients on treatment₂ in stratum $i, i = 1, \dots, u$

The estimated variance of $\hat{\delta}_{MH}$ is calculated as:

$$\widehat{var}(\hat{\delta}_{MH}) = \frac{\sum_{i=1}^u L_i}{(\sum_{i=1}^u w_i)^2}$$

$$\text{where } L_i = \frac{x_i(n_i - x_i) m_i^3 + y_i(m_i - y_i) n_i^3}{n_i \cdot m_i \cdot (n_i + m_i)^2}, i = 1, \dots, u$$

Assuming a normal distribution of $\hat{\delta}_{MH}$, an approximate 95% CI is given as follows, where $z_{0.975}$ is the 97.5% quantile of the standard normal distribution:

$$CI = \left[\hat{\delta}_{MH} \pm z_{0.975} \cdot \sqrt{\widehat{var}(\hat{\delta}_{MH})} \right]$$

Also, the approximate p-value can be calculated using the following:

$$\text{pvalue} = 2 \cdot \Pr \left[Z > \left| \frac{\hat{\delta}_{MH}}{\sqrt{\widehat{\text{var}}(\hat{\delta}_{MH})}} \right| \right], \text{ where } Z \sim N(0, 1)$$

If there is a stratum for a treatment group that has 0 patients in it, the 0 count will be replaced by 0.5 in order to prevent dividing by 0 in the above equations, as suggested in Greenland & Robins.

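### SAP 8.3.2 analyses 'micturitions < 8 at Week 12' with Sex as the only stratum, leaving out baseline micturitions and OAB Type and giving up precision on a supportive endpoint

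*SAP*

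**What the plan says.** SAP 4.3 lists the endpoint among the additional secondary endpoints: "Percent of all OAB patients with average number of micturitions < 8 per 24 hours at Week 12". SAP 8.3.2 makes it a cut-off on the Week 12 level alone: "A patient is defined as having an average of < 8 daily micturitions if the arithmetic mean of the number of micturitions per day" is less than 8. The analysis set is the FAS, so Wet and Dry patients are both included, and missing values are multiply imputed.

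For the test, 8.3.2 states "All of the above endpoints will be analyzed in the same manner as described above in" Section 8.2.3. That section specifies a "Cochran-Mantel-Haenszel risk difference estimate stratified by Sex (Female vs Male"), with a normal-approximation confidence interval and p-value. No other stratum or covariate is named.

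For the continuous form of the same diary variable, 8.1.1.1 states: "The analysis model will include terms for treatment, visit, OAB Type (Wet vs Dry), Sex (Female vs Male), Region (US vs non-US), baseline score", plus the visit-by-treatment interaction.

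Baseline comes from the run-in diary (6.3: "Baseline will be the data collected during the Run-in Period"). Under 5.5 and 6.3, a patient enters the FAS only with an evaluable change from baseline, which requires a baseline diary. SAP 3.9 makes OAB Type and Sex the two randomization strata. SAP 6.2 treats additional endpoints as supportive, with nominal p-values and no multiplicity adjustment.

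**The concern.** A percent-reduction responder is scaled to the patient's own starting value; this one is not. The diary definitions of OAB Wet and OAB Dry in 6.3 both require "An average of ≥ 8.0 micturitions per Diary Day; and", so the response cut-off sits at the entry boundary. A patient who starts at 8.5 responds with a fall of just over 0.5. A patient who starts at 14 needs a fall of more than 6. Baseline should therefore predict response strongly, and leaving it out puts that predictable variation into the standard error.

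The method in 8.2.3 was written for the FAS-I, which contains only Wet patients, so OAB Type has no role there; 8.1.2.1 gives that reason for dropping it from the UUI model. When 8.3.2 carries the method over to the full FAS, the reason no longer applies, yet OAB Type stays out.

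What is at stake is the width of the interval and the strength of the nominal evidence for one supportive endpoint.

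**Working it through.** **1. The SAP's own power figures (3.8).** Power = Φ(δ / (SD·√(2/n)) − 1.96).

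- Micturitions: 0.6 / (2.20·√(2/450)) = 0.6 / 0.1467 = 4.09; Φ(2.13) = 98.3%. SAP: 98%.
- UUI: 0.51 / (1.68·√(2/337)) = 0.51 / 0.1294 = 3.94; Φ(1.98) = 97.6%. SAP: 98%.
- Joint, uncorrelated: 0.983 × 0.976 = 96.0%. SAP: 96%.

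The inputs reproduce. The SAP states no power for the < 8 responder.

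**2. Model for the responder.** From the SAP: difference 0.6, SD 2.20, about 450 evaluable per arm, two-sided 0.05. Assumed, because the SAP gives none of it: baseline B is 8 plus a gamma variable with a chosen mean and SD; the slope s of Week 12 on baseline; the placebo change c.

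Placebo mean at Week 12 given B: μ(B) = B + c + (s − 1)(B − mean B).

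Response probabilities: q0(B) = Φ((8 − μ(B))/2.20) on placebo and q1(B) = Φ((8 − μ(B) + 0.6)/2.20) on vibegron. Their averages are P0 and P1, and d = P1 − P0.

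Central case: baseline mean 11.5, SD 3, s = 0.8, c = −1.5. On placebo:

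- B = 8.5: μ = 8.5 − 1.5 + 0.6 = 7.6, so q0 = Φ(0.18) = 57%.
- B = 14: μ = 14 − 1.5 − 0.5 = 12.0, so q0 = Φ(−1.82) = 3%.

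**3. Large-sample power, central case.** P0 = 0.276, P1 = 0.352, d = 0.076.

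- Without baseline: variance = [P0(1 − P0) + P1(1 − P1)]/n = (0.1998 + 0.2281)/450 = 0.000951; SE 0.0308; d/SE = 2.46; power Φ(0.50) = 69%. Sex has no prognostic weight in this model, so this also stands for the sex-stratified test.
- Standardised over baseline: variance = [E q0(1 − q0) + E q1(1 − q1)]/n + Var(q1 − q0)/(2n). The ratio of the two variances is 1.28, so the variance is 0.000951/1.28 = 0.000743; SE 0.0273; d/SE = 2.79; power Φ(0.83) = 80%.

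**4. Simulation.** 450 per arm, 15% male (the cap in 3.9), 2,000 trials per row, using the Mantel-Haenszel estimator and variance in 8.2.3. The logistic column is the test of the treatment coefficient with baseline and Sex in the model.

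| Baseline mean, SD | s | c | MH, Sex only | MH, Sex × baseline fifths | Logistic |
|---|---|---|---|---|---|
| 11.5, 3 | 0.8 | −1.5 | 72% | 81% | 82% |
| 11, 2.5 | 0.8 | −1.3 | 72% | 81% | 81% |
| 12, 3.5 | 0.8 | −2.0 | 65% | 78% | 79% |
| 11.5, 3 | 1.0 | −1.5 | 63% | 77% | 78% |
| 11.5, 3 | 0.6 | −1.5 | 76% | 83% | 82% |

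A linear risk-difference model with baseline and robust SE gained somewhat less (73% to 81% power). With no treatment effect, rejection was 4.5% to 5.2% for all four methods, including the SAP's.

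**5. Range over the assumptions.** Large-sample formula, 2 × 4 × 4 × 4 × 3 × 2 = 768 scenarios: n 450 or 500; baseline mean 10.5 to 12; SD 2.0 to 3.5; slope 0.5 to 1.0; placebo change −1.0 to −2.0; and 2.20 read as either the residual or the total SD of change. Gain in power from using baseline:

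- median 6.5 points
- middle half 4.0 to 10.7
- 5th to 95th percentile 2.3 to 16.5
- full range 0.4 to 19.7

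Every scenario gained. The gain is largest when Week 12 follows baseline closely and smallest when power is already near 100%. OAB Type was not modelled, so its contribution is not quantified.

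**The case against.** The strongest reply is that nothing here is invalid. The method is fully specified and holds its type I error. It yields a risk difference that sits naturally beside the tabulated counts. The endpoint is supportive, has no power target and gates nothing, and the same diary variable is tested with baseline adjustment as a co-primary. All of that stands, and it limits the weight of the point.

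The size also rests on inputs absent from the SAP. That stands too: the direction was the same in every scenario tried, but the size is an assumption-based range. The model further assumes that all baselines are at or above 8. The 'Missing' category of OAB-d Type in 6.3 allows that some run-in averages may fall below it.

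The multiple-imputation appendix and the list of changes from the protocol are not visible. Imputation may well use baseline, but that would not put baseline into the test.

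A reader might infer two stronger things. One is that chance baseline imbalance biases the result. It does not: under randomization it is sampling variation, which the stated SE covers. The other is that the argument extends to the 100% UUI responder in 8.2.3, third in the fixed sequence, so that formal testing of the four endpoints below it is put at risk. The documents do not support that. In a small simulation of that endpoint (600 trials per scenario, assumed baseline means of 2.5 to 3.5 episodes) the gains were only about 0 to 5 points. Several were not clearly different from zero, because each power figure carries a Monte Carlo error of about 1.5 points.

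**Conclusion.** The point holds as one of efficiency, confined to 'micturitions < 8' in 8.3.2. The sex-only analysis discards a strong predictor available for every FAS patient, and a randomization stratum, without a reason in the visible text. Under the SAP's 0.6, 2.20 and 450 per arm, and assumed baseline distribution, slope and placebo change, omitting baseline typically costs about 4 to 11 points of power. In the central case the sex-only test would need about 28% more patients for the same precision. No fixed loss can be claimed. The affected p-value is nominal, and the co-primary and key secondary conclusions do not change.

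**What to change.** In 8.3.2, before unblinding, give this endpoint its own analysis sentence in place of the bare reference to 8.2.3. Either of two forms serves:

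- a covariate-standardised risk difference from a logistic model with treatment, baseline average daily micturitions, OAB Type and Sex; or
- the existing Mantel-Haenszel risk difference with baseline quartile (cut-points from pooled, blinded data) and OAB Type added to Sex as strata.

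Keep the sex-only estimate as a sensitivity analysis. The reported quantity remains a difference in proportions, and no patient is lost.

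The cost is a few lines of text and code. The stratified form has 2 × 2 × 4 = 16 strata, some sparse. If both caps in 3.9 were reached and Sex and OAB Type were independent, the two arms would hold about 900 × 0.15 × 0.25 = 34 Dry males, or roughly 4 per arm in each quartile. The zero-count replacement in 8.2.3 might then be triggered; the logistic form avoids this. The analysis of the UUI responders in 8.2.3 can stay as it is.

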8.3.3. Patient Global Impression of Severity and Control

The Patient Global Impression (PGI) questions are designed to assess a patient’s overall impression of OAB, additional details are given in the [Appendix 3](#). The PGI-Severity and PGI-Control questions are ordinal assessments going from lower impact of disease to highest impact of disease with scales ranging from 1 to 4 for severity and 1 to 5 for control. These questions will be analyzed as categorical variables with count and percent for each category at Baseline, Week 4, Week 8, and Week 12. These questions will also be summarized descriptively as numerical variables of score and change from baseline at visits of Baseline, Week 4, Week 8, and Week 12. Finally, the change from baseline will be analyzed in the same manner using the MMRM described above in [Section 8.1.1.1](#).

[figure not shown]
[figure not shown]
The FAS will be the analysis set for the PGI analyses. For the MMRM analysis of change from baseline, no imputation of missing data will be performed.

[figure not shown]
8.4. Exploratory Efficacy Endpoints and Analyses Not Related to Primary/Secondary Endpoints

[figure not shown]

8.5. Exploratory Efficacy Endpoints and Analyses Not Related to Primary/Secondary Endpoints

8.6. ANALYSIS OF PHARMACOKINETICS

The full population PK analysis is beyond the scope of this SAP; only drug trough concentrations will be summarized.

Pharmacokinetic samples for PK Analysis will be collected from a subset of patients (approximately 25% of enrolled patients). Blood samples will be collected pre-dose at Week 4), Week 8, and Week 12 (at any time during the visit). Plasma PK concentrations will be listed and summarized by study visit using the PK population. Only concentrations collected between 22 and 26 hours post dose will be included in the summary statistics.

Missing concentration data for all patients who are administered scheduled study treatments will be considered as non-informative missing and will not be imputed. No concentration estimates will be provided for missing sample values.

- Concentration values below the assay's limit of quantification (BLQ) for pre-dose samples will be treated as zero.
- The sampling time relative to dosing for pre-dose samples will also be treated as zero.
- If the actual sampling time is missing, the planned time will be used.
- Samples taken far outside the sampling windows may be excluded from by-time point summary statistics. No further imputation will be applied to any missing values.

